5.5 Surgical Procedure

The surgical procedure for implantation of the Hybrid S-RW implant will be according to currently approved labeling as outlined in the surgical manual (P130016), specifically the procedure for a round window and/or extended round window insertion found on page 17 of the Nucleus® Hybrid™ L24 cochlear implant Cl24REH Surgeon's Guide.

The postoperative hospital stay will be determined by the subject's recovery with surgeon recommendation.

The surgeon is required to complete following each surgery:

A surgical questionnaire

5.6 Postoperative Procedures

5.6.1 Audiometric Testing

- Tympanometry, each ear
- Pure tone air-conduction hearing thresholds with insert earphones: 125, 250, 500, 750, 1000, 1500, 2000, 3000, 4000, 6000, 8000 Hz
 - Unilateral, each ear
- Bone conduction thresholds: 125⁷, 250, 500, 750, 1000, 1500, 2000, 4000 Hz
 - Unilateral, each ear

CONFIDENTIAL

⁷ Bone conduction measures at 125 Hz are optional based on potential audiometric equipment limitations.

Note: Clinician will need to confirm the subject's response to any pure tone stimulus presented at 125 and 250 Hz as auditory "heard" versus vibrotactile "felt" and record the response accordingly.

5.6.2 **Initial Activation**

5.6.2.1 **Sound Processor Fitting**

Initial activation will occur 4 weeks post-surgery, plus or minus 1 week. Threshold (T) and comfort (C) values will be determined for the electrical stimulation for each channel. Impedance telemetry results using common ground (CG) and monopolar (MP1, MP2 and MP1+2) stimulation modes will also be recorded. This information will be used to program the sound processor and also to monitor the device for possible degradation of function and/or damage to neural elements.

For subjects with preserved hearing, the basic programming approach will be to assign frequency channels to the electrode array that supplement the acoustic sensitivity. In other words, the frequency assignment of the electrical stimulation will begin at the frequency where acoustic hearing is no longer useful. For this purpose, hearing thresholds up to 90 dB HL will be considered not useful from an amplification perspective and not aidable acoustically.

An anonymous export of the test map will be sent to the Sponsor.

5.6.2.2 **Acoustic Component Fitting**

All patients will be fit with the Cochlear™ Nucleus® 6 Sound Processor (CP900 series). In the event that a subject retains aidable hearing, they will also be fitted with the acoustic component. The acoustic component will be appropriately fit using the same fitting algorithm as used preoperatively for hearing aid verification to assess the degree to which real-ear targets are met for each subject. Fitting methodology with the acoustic component is no different than that of conventional acoustic hearing aids.

Note: For any subject with aidable hearing post-surgery, the acoustic component should be fit. For postoperative testing, the best unilateral condition for the implanted ear will be the Hybrid Mode and the best bilateral condition will be the Combined Mode.

Note: For any subject with un-aidable hearing post-surgery, the best unilateral condition for the implanted ear will be CI alone Mode and the best bilateral condition will be the Bimodal Mode.

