3.2 Sound Processor Description

The Cochlear Nucleus 6 (CP900 series) sound processor (submitted under 970051/C096) as shown in Figure 3, is a behind the ear sound processor with a modular design that incorporates a main signal processing module (the "sound processor") with built-in directional microphones, a battery module (2-zinc air or rechargeable), radio frequency (RF) coil and coil cable.

Figure 3. Cochlear Nucleus 6 (CP900 series) Sound Processor

The Cochlear Nucleus 6 (CP900 series) sound processor can be programmed to provide electrical stimulation alone for patients with a total loss of acoustic hearing following implant surgery, or to provide both electrical and acoustic stimulation to cochlear implant recipients with postoperative audiometric thresholds between 125 and 2000 Hz measured within an aidable range (defined as air conduction thresholds up to 90dB HL). Due to the anticipated time needed to enroll and implant subjects it is possible that new sound processor technology may be introduced during the course of this clinical study. If new technology is released, is proven to be functionally equivalent to the Nucleus 6 Sound Processor, and demonstrates performance at least as good as that from the Nucleus 6 sound processor, subjects may be given the option to start with or upgrade to the new technology as part of this investigation.

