3.2.1 Acoustic Component

For recipients with postoperative audiometric thresholds up to 90dB through 2000 Hz, acoustic amplification can be delivered via an acoustic component which connects to the sound processor via a cable molded into the earhook of the speech processor, thereby delivering acoustic amplification in a similar way to a conventional hearing aid (Figure 4). The acoustic component is made up of the EAC200 Series Earhook and the EAC200 Series Power Speaker Unit that is worn in the ear (or functional equivalent paired with sound processor model). The Power Speaker Unit may be fit with either instant-fit disposable domes or customized hard acoustic components.

Figure 4. Acoustic Component Option for the Nucleus 6 (CP900 series) Sound Processor

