3.4 Programming Software Description

Programming of the sound processor is achieved via Cochlear Nucleus Custom Sound 4 (CS4) software, which is a modification of the existing, approved, Custom Sound software CS3. Cochlear Nucleus Custom Sound 4 software permits the characterization of both electric and acoustic parameters required for Hybrid simulation as in Custom Sound 2.1 (G070191). The general approach for the electric programming is the same as for Nucleus Hybrid L24 cochlear implant recipients. The software provides the ability to specify the cut-off frequency at which acoustic stimulation ends (e.g., thresholds up to 90 dB HL) and when electric stimulation begins. In addition, the software provides a user interface for the clinician to program amplification characteristics (gain and maximum output, frequency by frequency) for the low-frequency range of hearing, from 125 to 2000 Hz.

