4.1 Inclusion Criteria

- 1. Eighteen years of age or older at the time of implantation
- 2. Sensorineural hearing loss with the following requirements: a pure tone threshold less (better) than or equal to 60 dB HL at 500 Hz, less than (better) or equal to 80 dB HL at 1500 Hz, and high frequency severe to profound (a threshold average of 2000, 3000, & 4000 Hz) of > 60dB HL.
- 3. Minimum of 30 days experience with appropriately fit bilateral amplification, fit as described in the *Fitting and Use of Hearing Aids* section below
- 4. Aided monosyllabic word score (e.g., CNC Word Test) (mean of two lists) between 20% and 60%, inclusive (i.e., $20\% \le \text{score} \le 60\%$), in the ear to be implanted
- Aided monosyllabic word score (e.g., CNC Word Test) (mean of two lists) in the contralateral ear equal to, or better than, the ear to be implanted but not more than 80%
- 6. Willingness to use bimodal stimulation (i.e., a cochlear implant on one ear and a hearing aid on the contralateral ear) through 12-months postactivation
- 7. Ability to complete the required test materials.

4.2 Exclusion Criteria:

- Individuals aged greater than 75 years
- 2. Duration of severe to profound hearing loss (above 2kHz) greater than 20 years
- 3. Medical or psychological conditions that contraindicate undergoing surgery as determined by the Investigator
- 4. Ossification or any other cochlear anomaly that might prevent complete insertion of the electrode array
- 5. Conductive overlay of 15 dB or greater at two or more frequencies, in the range 500 to 1000 Hz
- 6. Deafness due to lesions of the acoustic nerve or central auditory pathway
- 7. Active middle-ear infection or tympanic membrane perforation in the presence of active middle ear disease
- Unrealistic expectations on the part of the subject, regarding the possible benefits, risks, and limitations that are inherent to the surgical procedure(s) and prosthetic devices as determined by the Investigator
- 9. Unwillingness or inability of the candidate to comply with all investigational requirements as determined by the Investigator

10. Additional handicaps that would prevent or restrict participation in the audiological evaluations as determined by the Investigator.

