5.4.1.2 Fitting and Use of Hearing Aids

Preoperatively, subjects will undergo candidacy testing using their own hearing aid devices. If a candidate does not own hearing aids, testing using loaner hearing aid devices may be provided by the candidate's hearing health provider.

Note: The speech perception criterion for enrollment into the study must be met with appropriately fit hearing aids, (both for the ear to be implanted as well as the non-implant ear), even if amplification proves to provide no measurable benefit over natural acoustic hearing for the particular subject.

To ensure standardization of hearing aid fitting, it is required that hearing aid settings for target and gain are set and verified. Real-ear measures are to be utilized to verify that the slope of the frequency response is within 5 dB per octave of the target slope.

During the fitting process, optimization of the response slope will be the priority for those frequencies where thresholds correspond to aidable hearing. Taking a conservative approach, aidable hearing will be defined by hearing thresholds up to 90 dB HL for this study.

It is recognized that prescriptive methods are based on average requirements, and that individuals may find deviations from target values optimal for sound loudness, quality, or clarity. For example, individual adjustments required to relieve occlusion effects will be permitted.

If the subject does not use hearing aids on a daily basis, does not own hearing aids, or uses hearing aids that are identified as inappropriately fit or poor functioning, the subject will undergo a hearing aid trial and/or readjustment period. The hearing aid trial period will be for a minimum of 30 days or longer as recommended by their study audiologist. At the end of the trial period, aided word recognition testing will be assessed to confirm that candidacy criteria are met.

Subjects will need to be willing to use bimodal stimulation (i.e. a cochlear implant on one ear and a hearing aid on the contralateral ear) through at least 12-months postactivation.

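### Section 5.6.2.1 states the 90 dB HL rule backwards: it calls not aidable the same thresholds that Sections 5.4.1.2 and 3.2 define as aidable

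*Protocol*

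**What the plan says.** Section 5.6.2.1 (Sound Processor Fitting) tells the site how to divide frequencies between acoustic and electric stimulation in subjects with preserved hearing. It first gives the principle: "the frequency assignment of the electrical stimulation will begin at the frequency where acoustic hearing is no longer useful". It then gives the cut-off for applying it: "hearing thresholds up to 90 dB HL will be considered not useful from an amplification perspective and not aidable acoustically".

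Four other places use the same 90 dB figure:

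- Section 5.4.1.2 (hearing aids): "aidable hearing will be defined by hearing thresholds up to 90 dB HL for this study".
- Section 3.2 (sound processor), for postoperative thresholds from 125 to 2000 Hz: "measured within an aidable range (defined as air conduction thresholds up to 90dB HL").
- Section 3.2.1 (acoustic component): "For recipients with postoperative audiometric thresholds up to 90dB through 2000 Hz, acoustic amplification can be delivered".
- Section 3.4 (software), more loosely: "cut-off frequency at which acoustic stimulation ends (e.g., thresholds up to 90 dB HL").

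The notes at the end of Section 5.6.2.2 use aidability to set the test conditions. With aidable hearing, the component is fitted and the best conditions are Hybrid and Combined. Otherwise, "For any subject with un-aidable hearing post-surgery, the best unilateral condition for the implanted ear will be CI alone Mode", and the best bilateral condition is Bimodal.

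**The concern.** The same number, unit and direction (thresholds up to 90 dB HL) receive opposite labels in the same protocol. The section with the wrong label is the one the audiologist works from at activation.

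Two things are at stake:

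- **The map.** The sentence sets the frequency at which electric stimulation begins. Applied as written, it moves that boundary into the region where the subject still hears well.
- **The listening condition.** Section 5.6.2.2 directly follows and depends on whether the subject has aidable hearing, but it does not restate the definition. The nearest statement of what is aidable is the inverted one. A subject with preserved hearing could be left without the acoustic component and tested as CI alone and Bimodal. Section 2.3 says that the best unilateral and best bilateral conditions are the ones used to evaluate performance with the implant, and monosyllabic words at 12 months are the primary efficacy measure.

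**Working it through.** The protocol gives no figure to reproduce here. The check compares the statements and then applies the literal rule to eligible subjects.

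**Step 1: the statements side by side**

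| Section | Thresholds up to 90 dB HL are |
|---|---|
| 5.4.1.2 | aidable, as the definition for the study |
| 3.2 | aidable, postoperatively, 125 to 2000 Hz |
| 3.2.1 | suitable for acoustic amplification, through 2000 Hz |
| 3.4 | tied to the acoustic cut-off; direction only loosely worded |
| 5.6.2.1 | not useful and not aidable |

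Three sections state one direction clearly, one is compatible with it, and 5.6.2.1 alone states the reverse. Nothing in the protocol says that 5.6.2.1 intends a different cut-off.

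**Step 2: which direction is possible**

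A lower threshold is better hearing. The principle in 5.6.2.1 is to start electric stimulation where acoustic hearing stops being useful, which is where thresholds are high. A rule that labels the low thresholds not useful defeats that principle, and it leaves thresholds worse than 90 dB HL without any label.

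**Step 3: the literal rule applied to eligible subjects**

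Inclusion criterion 2 requires "a pure tone threshold less (better) than or equal to 60 dB HL at 500 Hz", and 80 dB HL or better at 1500 Hz. Both limits lie below 90, so with no surgical loss at all both frequencies would be called not aidable in every eligible subject. For a subject exactly at the limits:

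- 500 Hz: 90 − 60 = 30 dB. Any postoperative loss of 0 to 30 dB leaves the threshold at or below 90 dB HL, so it is aidable under 5.4.1.2 and not aidable under 5.6.2.1.
- 1500 Hz: 90 − 80 = 10 dB. The same holds for any loss of 0 to 10 dB.

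The ears misclassified are therefore the best-preserved ones. A subject who enters with better thresholds has a wider margin still.

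**Step 4: speech scores exposed in the worst case**

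Section 5.6.3.3 lists five listening conditions for each of two tests (AzBio and CNC) at three visits (3, 6 and 12 months):

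- all conditions: 5 × 2 × 3 = 30 scores per subject;
- conditional ones (Acoustic Alone, Hybrid, Combined): 3 × 2 × 3 = 18;
- tested in everyone (Electric alone, Bimodal): 2 × 2 × 3 = 12.

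If the inverted rule also governed component fitting at every visit, the 18 conditional scores could be skipped. The other 12 would still be collected, but with a map built on the wrong frequency boundary.

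**The case against.** The strongest reply is that nobody would follow the sentence. Its own paragraph concerns subjects with preserved hearing and channels that add to it, and labelling every threshold up to 90 dB HL useless would leave nothing to add to. An audiologist programming a hybrid device would see the slip. The correct rule stands in 5.4.1.2 as the study definition, and in 3.2.1 for exactly the decision on the acoustic component. The faulty sentence is also limited to frequency assignment, so withholding the component requires a site to let it override the study-wide definition.

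There are safeguards as well. The map goes to the sponsor at activation, and again at later visits if settings are adjusted. There is one site, and no formal hypothesis is tested, so no error rate or power depends on the sentence.

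The count of 18 in 30 is also open to challenge, because it rests on Section 5.6.3.3. The schedule in Section 5.7 lists three postoperative conditions per test, or 3 × 2 × 3 = 18 entries in all. There the best-condition rows would be filled with Electric alone and Bimodal scores rather than left blank.

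Most of this stands, and it limits how serious the matter is. It does not make the text right. The limit to frequency assignment leaves the main error in place, because frequency assignment is where the rule does its work. The sentence also uses the word aidable, which 5.4.1.2 defines the other way. A site cannot comply with both sections.

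**Conclusion.** The contradiction is real, and Section 5.6.2.1 is the part that is wrong. It should be corrected, because it is an operative decision threshold for programming and not background description.

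On size, every threshold at or below 90 dB HL is classified in opposite ways by the two rules. That includes fully preserved hearing at 500 and 1500 Hz in every eligible subject. The direct risk is a wrongly placed acoustic-electric boundary. The further loss of up to 18 of 30 scores per subject assumes that the site applies the sentence literally, extends it to component fitting, does so at all three visits, and is not caught when the maps are reviewed. The protocol gives no basis for saying how many subjects this would touch, beyond the ceiling of 10.

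The primary endpoint is not left undetermined, because the intended rule can be recovered from 5.4.1.2 and 3.2. Sample size and error rates are not involved.

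**What to change.** In the quoted sentence of Section 5.6.2.1, replace *up to* with *above*, so that thresholds above 90 dB HL are the ones treated as neither useful for amplification nor aidable. One 90 dB HL rule then governs frequency assignment, acoustic-component fitting and choice of test condition, in line with 5.4.1.2 and 3.2.

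The cost is one phrase in the protocol, with no change to testing, sample size or analysis.

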5.6.2.3 Aided Audiometric Testing

Aided soundfield hearing thresholds: 125, 250, 500, 750, 1000, 1500, 2000, 3000, 4000
 Hz

In effort to monitor hearing preservation following the introduction of electrical stimulation, it is recommended that audiometric status be assessed on a weekly basis for 4 weeks

following initial activation. If a change in audiometric status is observed, please see Appendix E for associated steroid considerations.

5.6.3 **3, 6 & 12 Month Post Activation Evaluations**5.6.3.1 *Audiometric Testing*

- Tympanometry, each ear
- Pure tone air-conduction hearing thresholds with insert earphones: 125, 250, 500, 750, 1000, 1500, 2000, 3000, 4000, 6000, 8000 Hz
 - · Unilateral, each ear
- Bone conduction thresholds: 125⁸, 250, 500, 750, 1000, 1500, 2000, 4000 Hz
 - Unilateral, each ear

If sound processor settings are adjusted, an anonymous export of the test map will be sent to the Sponsor.

5.6.3.2 Aided Audiometric Testing

- Aided soundfield hearing thresholds: 125, 250, 500, 750, 1000, 1500, 2000, 3000, 4000
 Hz
 - Best unilateral condition, implanted ear with contralateral ear plugged

5.6.3.3 Speech Perception Testing

- S₀N₀ AzBio Sentences in Noise One list at 60 dB(A) with a +5 dB SNR lpsilateral Listening Conditions:
 - Electric alone (both ears plugged)
 - If applicable, Acoustic Alone (contralateral ear plugged)
 - If applicable, Hybrid (contralateral ear plugged)

Bilateral Listening Conditions:

- Bimodal (ipsilateral ear plugged)
- If applicable, Combined
- CNC Word Test (Quiet) Two lists at 60 dB(A)

Ipsilateral Listening Conditions:

- Electric alone (both ears plugged)
- If applicable, Acoustic Alone (contralateral ear plugged)
- If applicable, Hybrid (contralateral ear plugged)

Bilateral Listening Conditions:

⁸ Bone conduction measures at 125 Hz are optional based on potential audiometric equipment limitations.

- Bimodal (ipsilateral ear plugged)
- If applicable, Combined

Note: If the subject lost acoustic hearing in the implanted ear and does not utilize the acoustic component, the best unilateral condition is the same as electric alone and therefore does not need to be evaluated.

5.6.3.4 Questionnaires/Assessments

- Abbreviated Profile of Hearing Aid Benefit (APHAB)
- Speech Spatial and Quality (SSQ)12

5.7 Summary of Data Collection Visits

Test	Condition	Preoperative			Postoperative			
		Candidacy	Baseline	Surgery	Activation	3 Month	6 Month	12 Month
Informed Consent		Х						
Air Conduction Audiogram	Unilateral Each Ear	X			X	X	X	Х
Bone Conduction Audiogram	Unilateral Each Ear	х			Х	х	х	х
Aided Audiogram	Hearing Aid Unilateral Each Ear	X						
	Best Unilateral Implanted Ear) `		Х	If >10dB ▲ unaided	If >10dB ▲ unaided	If >10dB ▲ unaided
Tympanometry	Unilateral Each Ear	X			Х	Х	Х	Х
CNC words	Hearing Aid Unilateral Each Ear	х						
	Hearing Aids Bilateral		Х					
	Best Unilateral Implanted Ear					х	х	х
	Best Bilateral					X	Х	Х
	Electric Alone					X	Х	X
AzBio Sentences In Noise	Hearing Aid Ear to be Implanted		х					
	Hearing Aids Bilateral		Х					
	Best Unilateral					X	Х	Х

Cochlear						
	Implanted Ear					
	Best Bilateral			X	Х	X
	Electric Alone			X	Х	X
Surgical Questionnaire			Х			
Questionnaire						
APHAB		X		X	Х	Х
SSQ 12		X		X	Х	Х

6.0 Adverse Events

An Adverse Event (aka Adverse Effect or AE) is the development of an untoward medical occurrence or the deterioration of a pre-existing medical condition following or during exposure to an investigational product, whether or not considered causally related to the product or the surgical procedure to implant it. An untoward medical condition can be symptoms (e.g., nausea), signs (e.g., tachycardia, fever) or clinically significant abnormal results of an investigation (e.g., laboratory findings, chest x-ray).

Adverse events that occur during this study may be associated with the implant procedure, including adverse effects from general anesthesia, or specifically associated with the use of the device. An adverse event will be considered to be device-related when, in the judgment of the Primary Investigator, there is a logical connection between the use of the device and the occurrence of the event, above and beyond the study procedure itself.

A Serious Adverse Event (SAE) is any untoward medical occurrence which:

- Results in death;
- Is life-threatening;
- Requires in-patient hospitalization for > 24 hours or prolongation of hospitalization which is not specifically required by the protocol;
- Results in permanent impairment of a body function or permanent damage to a body structure; or
- Requires medical or surgical intervention to preclude permanent impairment of a body function or permanent damage to a body structure.

An unanticipated adverse device effect (UADE) is "any serious adverse effect on health or safety or any life-threatening problem or death caused by, or associated with, a device, if that effect, problem, or death was not previously identified in nature, severity, or degree of incidence in the investigational plan or application (including a supplementary plan or application), or any other unanticipated serious problem associated with a device that relates to the rights, safety, or welfare of subjects" [FDA 21 CFR 812.3(s)]. The Sponsor will promptly conduct an investigation upon notification by an Investigator of a UADE and will notify the FDA and all reviewing IRBs and participating Investigators within 10 working days after the sponsor first receives notice of the effect. Thereafter, the Sponsor will submit such additional reports concerning the effect as FDA requests.

For the purposes of this study, only unanticipated adverse device effects will be reported to FDA promptly following occurrence. Annual progress reports will contain information regarding SAE/AE occurrences.

